7.2 Subject Disposition and Data Sets Analysed

Subjects randomised will be summarised by country and site, and also summarised by aetiology of NDO (SCI or MS), and previous BTX-A usage (BTX-A naïve vs. BTX-A non-naïve in the bladder) for the Randomised population.

Statistical Analysis Plan

Version: Final v2.0

September-2018

Ipsen Protocol No. D-FR-52120-222

000000146259

Date of Issue: 21-

Covance Study ID:

The number of subjects screened but not randomised (screen failures) will be tabulated by country. The reasons for screen failures will be listed.

The randomisation details will be displayed in a listing for the Randomised population.

The number and percentages of enrolled subjects included in analysis populations (Randomised, Safety, mITT, and PP) will be summarised by treatment group and overall. The reason for subject exclusion from each of the populations will be tabulated and listed.

In addition, the number and percentage of subjects who completed the study, prematurely discontinued the study with primary reasons will be tabulated by treatment group in the Randomised population. The number of subjects entering, prematurely withdrawing with primary reasons will be tabulated by treatment group in the Randomised population for the DBPC Cycle and by Dysport Cycle. Subject disposition data, including retreatments after the first IMP administration, and study discontinuation will be listed.

7.3 Protocol Deviations

All protocol deviations will be listed for the Randomised population.

The protocol deviations, including defining those leading to exclusion from the PP population, will be identified before data are unblinded.

7.4 Demographics and Other Baseline Characteristics

Demographic and baseline characteristics will be listed and summarised for the mITT population.

Standard descriptive statistics including 95% confidence interval (CI) will be presented for the continuous variables of:

- Age (years)
- Weight (kg);
- Height (cm);
- Body mass index (BMI) (kg/m^2) calculated as $[\text{weight}(\text{kg})/(\text{height}(\text{cm})/100)^2]$

The total counts and percentages of subjects will be presented for the categorical variables of:

- Age groups [≥ 18 and ≤ 40 , >40 and ≤ 65 , > 65 years (further categorising to >65 and ≤ 75 , and >75 years))
- Sex (Male, Female);
- Race (Asian, Black or African American, White, Native Hawaiian or Other Pacific Islander, American Indian or Alaska Native and Other);
- Ethnicity (Hispanic/Latino, Not Hispanic/Latino);
- Stratification variables:
 - aetiology of NDO (SCI, MS)
 - previous intradetrusor BTX-A usage (BTX-A bladder naïve, BTX-A bladder non-naïve).
- Other baseline characteristics:

Statistical Analysis Plan

Version: Final v2.0

September-2018

Ipsen Protocol No. D-FR-52120-222

000000146259

Date of Issue: 21-

Covance Study ID:

- prior NDO oral medications (Yes, No)
- concomitant NDO oral medications at time of first IMP administration (Yes, No)
- prior treatment of anticholinergics (Yes, No)
- concomitant treatment of anticholinergics at time of first IMP administration (Yes, No)
- prior beta-3 agonists (Yes, No)
- concomitant beta-3 agonists at time of first IMP administration (Yes, No)
- daily CIC frequency at baseline
- history of UTI in the 6 months prior to study (Yes, No)
- using a wheelchair regularly in subjects with MS (Yes, No)

No formal tests of statistical significance will be performed on the demographic and baseline data. Other baseline data not only measured at screening will be summarised by treatment group with the post-baseline measurements.

The demographics and baseline characteristics data will also be summarised by aetiology of NDO (SCI, MS) for the mITT population.

Pregnancy test will be listed only.

7.4.1 UTI Prior to First IMP Administration

The counts and percentages of the following categories will be summarised for the mITT population:

- Overall subjects with UTI prior to first IMP administration
- Subjects with a medical history of UTI
- Subjects with a medical history of UTI within 6 months prior to screening
- Subjects with a recorded AE of UTI between informed consent and first IMP administration

7.4.2 Medical History

Medical History (significant medical or surgical history, NDO medical history for SCI and MS subjects) will be coded by Sponsor using the Medical Dictionary for Regulatory Activities [MedDRA v21.0 (March 2018); latest version if updated during the study). All medical history will be listed, and the number and percentage of subjects with any medical history will be summarised for the mITT population by system organ class (SOC) and preferred term (PT) for each treatment group and overall.

NDO Medical History will be summarised by aetiology of NDO (SCI, MS). Duration of NDO will be calculated as (informed consent date - date of development of NDO symptoms)*12/365.25 and reported as whole months, and presented using standard descriptive statistics.

For SCI history, percentage of neurological level of stable SCI, cause of stable SCI, American Spinal Injury Association (ASIA) Grade and neurological syndrome will be summarised.

Duration of SCI will be calculated as (date of the first IMP administration – date of stable SCI)*12/365.25 and reported as whole months, and presented using standard descriptive statistics.

For MS history, the percentage of level of mobility, classification of MS will be summarised. Duration of MS will be calculated as (date of the first IMP administration – date of initial diagnosis)*12/365.25 and reported as whole months, and presented using standard descriptive statistics. Duration of onset of symptoms will be calculated as (date of the first IMP administration – date of onset of symptoms)*12/365.25 and reported as whole months, and presented using standard descriptive statistics.

7.4.3 Prior and Concomitant Medications

Medications received prior to or concomitantly with treatment will be coded by Sponsor using World Health Organisation Drug Dictionary (WHO Drug Dictionary; Version B2-BDE March 2016 or a later version if updated during the study), and will be summarised by treatment group and overall with the number and percentage of subjects, by therapeutic class (the Anatomic Therapeutic Chemical [ATC] Classification codes) and preferred term. The concomitant medications and therapies will be summarised separately for the DBPC Cycle and by Dysport Cycle (Dysport Cycle 1, 2, etc).

Prior medications and concomitant medications are defined as follows:

Prior medications/non-drug therapies are those taken within 30 days prior to screening with a stop date prior to the date of the first IMP administration. Prior medications or therapies for NDO are those with both start date and stop date prior to the date of the first IMP administration.

Concomitant medications are those with a start date on or after the date of the first IMP administration, or those with a start date before the date of the first IMP administration and a stop date on or after the date of the first IMP administration (or ongoing).

Prior medications and concomitant medications will be listed together and summarised separately for the mITT population. Similarly, this will be listed and summarised for the prior and concomitant medications for NDO, and for prophylactic antibiotic for initial treatment, retreatments and urodynamic assessments.

Concomitant Surgical Procedures will be summarised by SOC and PT for the mITT population.

7.5 Treatment Exposure

Treatment exposure will be summarised descriptively by treatment group (placebo, Dysport 600 U, Dysport 800 U, All Dysport) in the Safety population. IMP administration data will be listed for the Safety population.

The treatment exposure will be summarised by number and percentage of subjects treated in each treatment cycle (DBPC cycle, Dysport Cycle 1, Dysport Cycle 2, etc), the number of Dysport Cycles will be displayed descriptively using summary statistics for the Safety population.

The treatment exposure in weeks will be summarised by treatment group as below:

For overall study (irrespective of number of treatments)

- Total IMP exposure across the study will be calculated as (Last attended visit date in the study – first IMP administration date + 1) / 7. Data will be presented in weeks for placebo, 600 U Dysport, 800 U Dysport, All Dysport groups.

- The number of subjects cumulatively exposed to IMP for at least 12 weeks, 24 weeks, 52 weeks, 78 weeks and 104 weeks will be summarised for placebo, 600 U Dysport, 800 U Dysport and All Dysport groups.
- Total Dysport exposure across the study will be calculated as (Last attended visit date in the study - first Dysport injection date + 1) / 7. Data will be presented in weeks for 600 U, 800 U and All Dysport groups.
- The number of subjects cumulatively exposed to Dysport at least 12 weeks, 24 weeks, 52 weeks, 78 weeks and 104 weeks will be summarised. Data will be presented in weeks for 600 U, 800 U and All Dysport groups

For Dysport Cycles

- The total number of subjects who received 1, 2, 3, ...etc and at least 1, 2, 3...etc Dysport treatments at 600 U, 800 U and All Dysport will be summarised .

7.6 Efficacy

The primary analysis based on the primary efficacy endpoint (mean change from study baseline in weekly number of UI episodes at Week 6 after the first IMP administration) will be performed on the mITT population.

7.6.1 Significance Testing and Estimations

The primary efficacy hypotheses are as follows:

- 1) Ho: There is **no** difference between treatment with Dysport 600 U or Dysport 800 U and treatment with placebo with respect to the change from baseline to Week 6 after the first study treatment in the number of UI episodes per week.
- 2) Ha: There **is** a difference between treatment with Dysport 600 U or Dysport 800 U and treatment with placebo with respect to the change from baseline to Week 6 after the first study treatment in the number of UI episodes per week.

7.6.2 Multiplicity Adjustment

For the primary endpoint, due to multiple pairwise comparisons of each Dysport dose group versus placebo, a Hochberg correction will be applied to control the type one error at 5% significance level. The p-values from the two pairwise tests are ordered in magnitude from largest to smallest.

If both p-values for the two primary tests (the test of 600 U vs. placebo and the test of 800 U vs. placebo) are lower than 0.05, both will be declared statistically significant. If one of the primary tests has a p-value greater or equal to 0.05, then the other test will be declared statistically significant if its p-value is lower than 0.025 (and thus half of the overall experiment wise alpha of 0.05).

The six ordered secondary endpoints will be tested for both doses at the 0.05 level (using a hierarchical methodology) if, for both doses, the two primary tests achieve a p-value lower than 0.05. If one of the primary tests has a p-value greater or equal to 0.05, and the other has a p-value lower than 0.025, secondary endpoints will be assessed (using hierarchical methodology) for the dose group with p-value lower than 0.025, at the 0.025 significance level.

In order to control the family-wise type one error, the following hierarchical testing procedure will be applied for the testing of the superiority of both Dysport doses to placebo for the primary and selected secondary endpoints (ordered as described in Section 7.6.5):

- Step 1: The Dysport 600 U and Dysport 800 U will be compared to placebo on the primary endpoint. If the p-values associated with both doses are <0.05 then both doses will be declared statistically significant and the testing will proceed at the 0.05 level from step 2 onwards. If one dose has $p \geq 0.05$ but the other has $p < 0.025$ (significant dose) then testing will proceed at the 0.025 level from step 2 onwards on the significant dose only. If both dose groups have $p \geq 0.05$ or one dose group has $p \geq 0.05$ and the other dose group has $p \geq 0.025$, the testing procedure will be stopped.
- Step 2: The Dysport 600 U and Dysport 800 U will be compared to placebo for the first hierarchical secondary endpoint. Testing will be at the significance level defined in step 1 (0.05 or 0.025). If the p-value associated with this test is lower than the significance level defined in step 1 then it will be considered significant and testing will proceed to step 3. Otherwise the testing procedure will be stopped.
- Step 3: Up to a further five steps will be performed, in each case testing the second through sixth hierarchical secondary endpoints in sequence. Testing will be conducted in the same manner as for the first hierarchical secondary endpoint. Significance testing will only proceed to the next hierarchical endpoint if the test is considered significant for each respective endpoint.

The above testing rules ensure that the hierarchical procedure controls the experiment-wise type one error (i.e. over the seven tests) at the 0.05 level for relevant secondary endpoints.

In the event the hierarchical testing procedure is stopped at the end of any particular step, the testing of the following steps will be considered descriptive only and no formal statistical conclusion will be drawn.

Each other secondary endpoint not included within the hierarchical testing procedure will be analysed for exploratory purposes only to compare each Dysport dose to placebo at a 0.05 type one error rate.

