9.3 Significance Testing and Estimations

All statistical tests will be performed two-sided with a type one error rate set at 5%.

Experiment-wise control of type one error for the primary endpoint will be performed using a conservative approach. The primary efficacy hypotheses are as follows:

- 1) Ho: There is **no** difference between treatment with 600 U or 800 U Dysport[®] and treatment with placebo with respect to the change from pretreatment to Week 6 after the first study treatment in the number of UI episodes per week
- 2) Ha: There **is** a difference between treatment with 600 U or 800 U Dysport[®] and treatment with placebo with respect to the change from pretreatment to Week 6 after the first study treatment in the number of UI episodes per week.

For the primary endpoint, due to multiple comparisons of more than two treatments, a Hochberg correction will be applied to control the global type one error at 5% significance level. If both p-values for the two primary tests (the test of 800 U vs. placebo and the test of 600 U vs. placebo) are lower than 0.05, both will be declared statistically significant. If one of the primary tests has a p-value greater or equal to 0.05, then the other test will be declared statistically significant if its p-value is lower than 0.025 (and thus half of the overall experiment wise alpha of 0.05).

The six ordered secondary endpoints will be tested for both doses at the 0.05 level (using a hierarchical methodology) if, for both doses, the two primary tests achieve a p-value lower than 0.05. If one of the primary tests has a p-value greater or equal to 0.05, and the other has a p-value lower than 0.025, secondary endpoints will be assessed (using hierarchical methodology) for the dose group with p-value lower than 0.025, at the 0.025 significance level.

In order to control the family-wise type one error, the following hierarchical testing procedure will be applied for the testing of the superiority of both Dysport[®] doses to placebo for the primary and selected secondary endpoints (ordered as described in [Section 3.2.2.2](#)):

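### The secondary hierarchy does not hold experiment-wise error at 5% across two doses: up to 9.1–9.75% if doses are claimed separately, up to 7.4% even if both must pass

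*SAP*

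**What the plan says.** Each dose is compared with placebo on the primary endpoint (weekly UI episodes at Week 6), where "a Hochberg correction will be applied to control the type one error at 5% significance level". What follows depends on the result (SAP 7.6.2; same rules in Protocol 9.3 and, without the numbered steps, in the protocol synopsis):

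- Both primary p-values below 0.05: "The six ordered secondary endpoints will be tested for both doses at the 0.05 level".
- One p-value at or above 0.05 and the other below 0.025: "testing will proceed at the 0.025 level from step 2 onwards on the significant dose only".

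The family covers both doses, since the procedure "will be applied for the testing of the superiority of both Dysport doses to placebo for the primary and selected secondary endpoints". The rule for passing a secondary step is in the singular: "If the p-value associated with this test is lower than the significance level defined in step 1 then it will be considered significant". Both documents then state that these rules give a procedure that "controls the experiment-wise type one error (i.e. over the seven tests) at the 0.05 level for relevant secondary endpoints".

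**The concern.** A fixed sequence protects 5% within one chain of tests. Here there are two chains, one per dose, and the plan adjusts for having two doses only at the primary. There are two ways for error to exceed 5%. They are alternatives and do not add.

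- **Route 1, both doses win the primary.** Each dose gets the full 0.05 on every secondary, with no split between doses.
- **Route 2, only one dose works on UI.** Hochberg has already tested the losing dose at 0.05, so no alpha is left to carry forward, yet the winning dose's secondaries get another 0.025.

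Step 2 also compares two doses but speaks of one p-value. It does not say what happens when one dose passes and the other fails. If that is settled after unblinding, the results can choose the reading.

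At stake are the confirmatory claims on MCC, MDP, Vol@1stIDC, continence, absence of IDCs and I-QoL. The secondaries already labelled exploratory are not affected.

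**Working it through.** **Inputs**

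- Two-sided tests, overall 0.05 (Protocol 9.3); secondary levels 0.05 or 0.025 as above (SAP 7.6.2).
- Treatment 1 allocation 1:1:1 with placebo pooled (Protocol 9.2; SAP 2.2). With equal arms and a shared placebo, the two dose contrasts each have variance 2σ²/n and covariance σ²/n, so the test statistics correlate at 0.5.
- Planned difference 21 − 12 = 9 episodes, SD 20, dropout 10%, 110 per arm (SAP 2.2 and 2.3).
- Assumed: correlation between endpoints of 0, 0.3 or 0.6, because the documents give none; normal test statistics.

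**1. Where the 5% figure is right.** In one dose's seven-test chain at 0.05, the first true null is rejected with probability 0.05 at most, so the chain is controlled. Hochberg on the two primary tests alone, global null, correlation 0.5: 0.048. The primary is controlled.

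**2. Route 1: both doses effective on UI, primary power near 1**

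- First secondary null for both doses, doses claimed separately: P(either) = 0.05 + 0.05 − P(both) = 0.10 − 0.0093 = **0.0907**.
- 600 U null on one secondary and 800 U null only on a later one, other steps passed almost surely: the two tests correlate at 0.5 times the endpoint correlation. For endpoint correlation 0 / 0.3 / 0.6 the result is **0.0975 / 0.0969 / 0.0951**; the first is 1 − 0.95².
- If both doses must pass a step: 0.0093 with both null, 0.050 with one null. Route 1 then stays within 5%.

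**3. Route 2: 600 U null on UI; 800 U effective on UI (power near 1) but null on the first secondary**

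- With probability 0.05, 600 U has p < 0.05 and is falsely declared on the primary.
- Otherwise (0.95) 800 U wins alone and its first secondary is tested at 0.025.
- Total with independent endpoints: 0.05 + 0.95 × 0.025 = **0.0738**.
- Simulation for endpoint correlation 0 / 0.3 / 0.6: 0.0739 / 0.0735 / 0.0722. The pass rule makes no difference, because the excess arises where only one dose is being tested.

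**4. At the planned effect.** Evaluable per arm: 110 × 0.9 = 99. Noncentrality: 9 / (20 × √(2/99)) = 9 / 2.843 = 3.17. Both doses win the primary in 81.1% of trials and exactly one in 12.2%.

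| Setting | Doses claimed separately | Both must pass |
|---|---|---|
| Route 1, primary power near 1 | 9.1–9.75% | 0.9–5.0% |
| Route 2, primary power near 1 | 7.2–7.4% | 7.2–7.4% |
| Route 1, planned effect, first secondary null for both doses | 6.2–7.7% | about 1% |
| Route 2, planned effect | 5.8–6.5% | 5.8–6.5% |

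**5. Error under two replacement rules**

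| Rule | Route 1 | Route 2 | Planned effect (Route 1) |
|---|---|---|---|
| Hochberg at every step, stop unless both doses pass | 4.8% | 5.0% | 3.1–3.9% |
| One chain per dose at 0.025 | 4.6–4.7% | 4.8–4.9% | 2.9–3.9% |

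The first rule is valid because getting past any step that contains a true null already requires a false rejection there. The overall error is therefore that of one Hochberg test. Across all seven endpoints, in 60 random patterns of null and real effects, it stayed at 5% within simulation error.

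**The case against.** The strongest defence reads Step 2 as a joint gate: one decision per endpoint, passed only if both doses pass. That fits the singular p-value and the count of seven, and it brings Route 1 within 5%.

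On Route 2, the defence notes that 5.0 of the 7.4 points are a false primary claim for the null dose, at its permitted level; only about 2.4 points are added by the lone dose's secondaries. If the guarantee is taken to cover false secondary claims only, and the joint gate applies, no setting examined exceeded 5% beyond simulation error. The headline figures also need primary power near 1.

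Much of this stands as qualification. The figures are maxima, the 7.4% must be read with its split, and the 9.1% depends on separate claims. It does not rescue the sentence. The joint gate is not written anywhere. The guarantee is called experiment-wise over seven tests, and one of the seven is the primary, so a false primary claim counts. Strong control has to hold in every configuration, and at the planned effect both routes still exceed 5%, Route 1 under separate claims and Route 2 under either pass rule.

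**Conclusion.** The concern holds and must be fixed. The statement of 5% experiment-wise control is wrong as written in both documents. With doses claimed separately the error reaches 9.1% (same null endpoint) to 9.75% (nulls at different steps), all of it on the secondaries. With a joint gate it still reaches 7.4% when only one dose works on UI. At the design assumptions the corresponding figures are 6.2–7.7% and 5.8–6.5%.

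The correlation of 0.5 between doses follows from the design; endpoint correlation of 0 to 0.6 is assumed, and the conclusion does not depend on where in that range it lies. Control of the two primary tests, and of one dose's chain taken alone, is intact.

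**What to change.** In SAP 7.6.2, Protocol 9.3 and the synopsis:

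1. Keep Hochberg for the primary.
2. If both doses win, apply Hochberg at 0.05 across doses at each secondary step (both p < 0.05, or the smaller p < 0.025). Go to the next endpoint only if both doses are significant, and state what happens when one passes and one fails.
3. If only one dose wins the primary, report its secondaries descriptively.
4. Replace the count of seven with the actual family of 14 dose-by-endpoint hypotheses.

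Only lowering the two-dose secondary level to 0.025 is not enough: the one-dose case stays at 7.3–7.4%.

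**Cost.** Text changes only, no extra patients, primary power unchanged; SAP section 1 allows amendments before database lock. It does change the confirmatory strategy, with three losses:

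- A lone dose with p between 0.025 and 0.05 on a secondary loses that claim.
- One dose failing a step ends formal testing for the other. Exactly one dose falls below 0.05 in 8–23% of trials per step, at an assumed 95–80% power per dose on that endpoint; this includes the trials in the previous item.
- All six secondaries become descriptive in the 12% of trials, at the design effect, in which one dose wins the primary.

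**Alternative.** A separate seven-endpoint fixed sequence per dose at 0.025, the alpha used for the sample size, is equally valid. It avoids the last two losses, but the chance that both doses win the primary falls from 81% to 72%. The choice is the sponsor's; either one must be fixed before unblinding.
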